3 VARIABLE IN THE ANALYSIS

3.1 DEMOGRAPHY AND BASELINE CHARACTERISTICS

The following demographic variables are recorded and evaluated: age and gender. It also detects whether a (pseudo) allergy to silicone or sweat is present. Concomitant diseases are recorded and listed.

Physical features such as height, weight, BMI, chest circumference on day 1 and vital signs (systolic and diastolic blood pressure, heart rate) are displayed with mean and standard deviation.

If necessary, systolic and diastolic blood pressure and heart rate are recorded and displayed on the following day.

Problems with skin before applying the belt are detected.

The characteristic "one-lung ventilation patient" (OLV) or not (ICU) is recorded and evaluated.

If applicable, it is additionally subdivided into Double Lumen Tube (DLT) / Bronchus Blocker (BB) or others.

Electrode belt details such as size, closure position (plughole), belt application in accordance with the clinical investigation plan, electrode mode and signal quality are recorded.

The reasons, why the intervention or surgical procedure has to be done are listed separately according to OLV and ICU group.

The baseline parameters also include the basic data of the ventilation procedure, such as saturation of s_aO_2 , s_pO_2 , p_aO_2 , p_aCO_2 , FiO_2 before and after the intervention. Depending on the distribution, they are determined as mean and standard deviation or as median and percentiles.

If present, auscultation findings, imaging findings (CT, X-ray, or ultrasound) before and after the intervention and the radiological findings are recorded and listed. These findings were collected for the duration of the study (day -2 - day +3).

3.2 PRIMARY STUDY OBJECTIVE

3.2.1 Efficacy

It should be demonstrated that PulmoVista 500 is able to monitor ventilation with the associated interventions of a patient. The global impedance waveforms of PulmoVista 500 should be comparable to the volume waveforms of the ventilator. For this purpose, the cross-correlation coefficient between these two waveforms is calculated twice per patient (before and after an intervention) for all 80 patients.

3.3 SECUNDARY STUDY OBJECTIVES

3.3.1 Efficacy

- To demonstrate the ability of PulmoVista 500 to display regional ventilation changes, a quantitative evaluation is performed using the cross-correlation coefficient between the impedance waveforms of PulmoVista 500 and the ventilator volume waveforms in the subgroup of OLV patients.
- To evaluate Pulmo Vista 500's monitoring features, it assesses whether changes in tidal volumes induced by ventilation settings are represented by the "main view". For this purpose, the plausibility questionnaire is evaluated.

- Assess that changes of the end-expiratory lung volumes (induced by e.g. PEEP changes, recruitment and suctioning maneuvers) can be monitored by “dEELI trend view”. The plausibility questionnaire is also evaluated for this.
- To evaluate the clinical usefulness of PulmoVista 500, the questionnaire on clinical utility across all patients is evaluated.
- In order to demonstrate the ability of PulmoVista 500 to produce controlled induced regional changes, an evaluation is performed using the OLV subgroup. Three blinded rater evaluate the corresponding waveforms.

3.3.2 Safety

A documentation of all safety-related events related to the use of PulmoVista 500 is provided.

4 TREATMENT OF MISSING, UNUSED OR SPURIOUS DATA, INCLUDING DROP OUTS AND WITHDRAWALS

4.1 MISSING VALUES

No missing data imputation techniques will be applied, and patients with missing efficacy data will be used as censored in the time to event analysis. Therefore any effort should be undertaken to avoid missing data, notably in case of the primary outcome measures.

When a patient is withdrawn from the trial before the scheduled end of a treatment phase, and an end-of-study visit can be performed, the data of this visit will be used for computing the primary outcome measure.

The handling of missing data will be specified in the Data Review Meeting.

Only data from patients for whom appropriate ventilation waveforms are available can be evaluated. Patients without evaluable ventilation waveforms are drop-outs.

4.2 OUTLIERS

Outlier criteria, especially for peaks in the impedance waveform, are set in the Data Review Meeting. These criteria decide on an additional evaluation collective without these outliers.

5 STATISTICAL ANALYSIS

5.1 PARTICIPANTS

A sample size of n=80 patients (including at least 25 patients for the OLV subgroup) has been calculated with an assumed drop-out rate of 15%.

OLV subgroup consists of patients who have been scheduled for surgical procedures that require the ventilation of only one lung (e.g., intubation using a double-lumen tube or placement of a bronchus blocker).

The remaining 55 patients are patients mechanically ventilated in an intensive care unit (ICU) via an artificial airway access (endotracheal tube or tracheostomy tube). For those, it can be assumed that significant changes to the ventilation settings will have to be made, which are continuously recorded with the PulmoVista 500 during the study.

5.2 DEMOGRAPHY AND BASELINE CHARACTERISTICS

The features of Chapter 3.1 are presented according to their distribution characteristics.

5.3 PREMEDICATION, CONCOMITANT MEDICATIONS AND PRE-DISEASES

All recorded pre-diseases and concomitant medications were listed.

5.4 EXPOSURE TO THERAPY/COMPLIANCE

Attention must be paid to patients with (pseudo-) allergies to sweat or silicone.

5.5 PRIMARY ANALYSIS

The basic data for the analysis is recorded in a database. The ventilation data for both waveforms- the global impedance waveforms and the volume waveforms- are stored for each patient in a cloud and prepared using a statistical analysis algorithm (see Appendix 7.2 Workflow for determining the time ranges used to calculate the cross correlation between the global impedance waveform (PulmoVista 500) and the volumetric waveform (Evita V500)).

The two EXCEL tables per patient contain the two waveforms to be compared (Appendix 7.2, Section 14, Columns A, B, C and N). From this, two cross-correlation coefficients per patient were calculated. The cross-correlation coefficients are a measure of the relationship between the two waveforms.

Figure 1 shows a section of both waveforms unstandardized. The numbers and diagrams are examples from the study „Assessment of the capability of PulmoVista 500 to

continuously monitor regional ventilation distribution and its changes over time",
Investigation reference number PulmoVista 500-30022.

[figure not shown]

Fig. 1: PulmoVista 500 Impedance Waveform (Global- blue) and Reference Volume Waveform (RTD_Vol_mL- green) unstandardized over time

If you standardize both waveforms, you get the following figure:

[figure not shown]

Fig. 2: PulmoVista 500 Impedance Waveform (Global- blue) and Reference Volume Waveform (RTD_Vol_mL- green) standardized over time

Figure 2 shows a slight time shift of the waveforms to each other.

In this example there is e.g. a correlation coefficient (Pearson) of 0.871 for the waveforms. Taking into account the shift (here Lag = 10: Shift from one curve to the other by 10 measuring times in both directions from 0) it results in a cross-correlation coefficient of 0.995.

To refute the hypothesis of independence of both waveforms, it has to be shown that the global impedance waveforms (as measured by the PulmoVista 500) and the global volume waveforms (of the EvitaV500 ventilator) correlate significantly (rejection of the null hypothesis "no correlation"). Because 2 experimental steps (before and after each intervention) should be performed in 80 patients, 80 averaged (from the pre- and post-values) cross-correlation coefficients will be obtained in total. If, for technical reasons (for example, incorrectly set markers), there are only pre- or post-values, the averaging in this patient is omitted and only one cross-correlation coefficient is used. From these averaged cross-correlation coefficients, a 95% confidence interval is calculated and a one sample t-test is performed to determine if the mean of the cross-correlation coefficients is significantly different from zero.

The significance level is $\alpha = 0.05$.

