7 STATISTICAL CONSIDERATIONS

7.1 SAMPLE SIZE, DROP-OUT-RATES, LEVEL OF SIGNIFICANCE AND POWER OF THE CLINICAL INVESTIGATION

Primary Endpoint (Efficacy)

Based on former porcine trials⁷ with PulmoVista 500 and data from clinical studies with other EIT devices the sample size was calculated using the program G*Power 3.1.9.2.

An α -error of $p = 0.05$ and a power = 0.9 in a two-sided testing resulted in a sample size of 68 patients. With this sample size a difference of 0.1 of the mean cross-correlation coefficient shall be detected, i.e. the true value of a calculated mean of 0.8 will not be smaller than 0.7 and not be larger than 0.9 with the given p-value and power under the assumption of a standard deviation of less than .25.

Accounting for 15 % potential drop-outs 80 patients shall be enrolled in the study.

Secondary Endpoint (Efficacy)

Based on former porcine trials with PulmoVista 500 and data from clinical studies with other EIT devices the sample size was calculated using the program G*Power 3.1.9.2. An α -error of $p = 0.05$ and a power = 0.9 in a two-sided testing resulted in a sample size of 22 patients. With this sample size a difference of 0.1 of the proportion between reference and investigated variable shall be detected.

Accounting for 15 % potential drop-outs 25 patients shall be enrolled in this subgroup of the study.

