7.2 STATISTICAL DESIGN

Null-Hypothesis

The PulmoVista 500 is not capable of continuously monitoring ventilation.

Primary Endpoint (Efficacy)

To assess the capability of PulmoVista 500 for continuous monitoring of ventilation and its changes at different points in time during varying states of regional ventilation, the cross-correlation function (CCF) between global tidal impedance (EIT) waveforms and global tidal volume (ventilator) curves will be evaluated.

- To refute the null-hypothesis of this trial it must be shown that the global tidal impedance waveforms and the global tidal volume curves correlate

⁷ Fischer E, Gremse F. Assessment of the capability of PulmoVista® 500 to continuously monitor regional ventilation distribution and its changes over time. An Animal Study. FINAL STUDY REPORT. PulmoVista 500-30022. Aix Scientifics. 2016-01-27

significantly, i.e. that the correlation scores are significantly different from zero.

- If the null-hypothesis is refuted the capability of PulmoVista 500 is assumed to be a valuable diagnostic device for long-term monitoring of mechanical ventilation.

The mean value of the intra-subject cross-correlation function (CCF) between global impedance (EIT) waveforms and global volume (ventilator) curves will be determined.

Secondary Endpoint (Efficacy)

To assess the capability of PulmoVista 500 to detect regional changes of ventilation it shall be tested, whether EIT can correctly differentiate between normal and single-lung ventilation.

- To refute the null-hypothesis of this trial it must be shown that the regional information about tidal impedance variation matches the clinical changes from normal to single-lung ventilation, i.e. that EIT detects ventilation vs. no ventilation in each lung.
- If the null-hypothesis is refuted the capability of PulmoVista 500 is assumed to be a valuable diagnostic device for detecting regional ventilation changes during long-term monitoring of mechanical ventilation.

The diagnostic output of the EIT measurements will be compared with clinical ventilation settings in a 2x2 table.

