7.3 PASS/FAIL CRITERIA

There is no pass/fail criteria defined.

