5.6 SECUNDARY ANALYSIS

5.6.1 Efficacy

- To demonstrate the ability of PulmoVista 500 to visualize regional ventilation changes, a quantitative evaluation is performed by calculating the cross-correlation coefficients between the impedance waveforms of PulmoVista 500 and the ventilator volume waveforms of OLV patients. The evaluation is carried out as in the primary analysis.
- In addition, a qualitative evaluation of the regional changes will be carried out. To do so, three blinded raters compare the corresponding sections of all OLV patients independently. Based on the information from the PulmoVista 500 video sequence provided, the raters evaluate which of the two halves of the lung is ventilated. The results are entered patient-related (pseudo-patient number) in the following table by the rater:

Pseudo-Patnr.	Valuation	
1	1	
2	2	
3	0	
4	1	
.	.	

Description of valuation:	0	not assessable
	1	right ventilated / left blocked
	2	left ventilated / right blocked

Tab. 1: Example of table for the qualitative evaluation of the OLV patients and the associated rating

The PulmoVista 500 video sequences to be assessed are created according to a workflow (see Appendix 7.3 Workflow for the creation of OLV videos) and made available to the raters. The pseudo-patient numbers are randomly generated by lot. These three tables of the raters will be merged into the KKS. A decision is considered positive or negative if at least two raters have come to the same result. In the opinion of one or more raters, is it not possible to judge the waveform (Code 0), the following assignment applies:

1x not evaluable & 2x same decision -> clear assignment in the table,
 1x not assessable & unequal decision of the remaining 2 raters -> drop out,
 2x or 3x not evaluable -> drop out.

A 2x2 Table will be created in the following form from the 3 tables of the raters (one of each rater):

Reference	Evaluation of the raters (with information provided by PulmoVista 500)	
	right ventilated / left blocked	left ventilated / right blocked
right ventilated / left blocked	a	b
left ventilated / right blocked	c	d

Tab. 2: Table for the accordance of rater and reality of the OLV patients

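### The primary test compares the mean cross-correlation only with zero, which cannot carry the diagnostic-value conclusion that Protocol 7.2 draws from it

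*SAP*

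**What the plan says.** **Aim.** SAP 3.2.1: "The global impedance waveforms of PulmoVista 500 should be comparable to the volume waveforms of the ventilator".

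**Sizing.** Protocol 7.1 uses a two-sided test at 0.05 with power 0.9 and an SD below 0.25, and arrives at 68 evaluable patients (80 enrolled). It explains the target as follows: "the true value of a calculated mean of 0.8 will not be smaller than 0.7 and not be larger than 0.9".

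**Test.** Protocol 7.2 requires only "that the correlation scores are significantly different from zero". SAP 5.5 implements this on one coefficient per patient, normally the average of a pre- and a post-intervention value: "a one sample t-test is performed to determine if the mean of the cross-correlation coefficients is significantly different from zero". It adds an interval: "From these averaged cross-correlation coefficients, a 95% confidence interval is calculated". SAP 5.5 describes rejection only as refuting the absence of correlation.

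**Conclusion.** Protocol 7.2 goes further: "If the null-hypothesis is refuted the capability of PulmoVista 500 is assumed to be a valuable diagnostic device for long-term monitoring". Protocol 7.3 states: "There is no pass/fail criteria defined".

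**Secondary use.** For the one-lung-ventilation (OLV) coefficients, SAP 5.6.1 says: "The evaluation is carried out as in the primary analysis".

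**The concern.** The sizing, the test and the conclusion refer to three different things. The sizing concerns a mean near 0.8, give or take 0.1. The test asks whether the mean is zero. The conclusion is about diagnostic value over long-term use. Rejecting zero says that the two waveforms are not unrelated on average. It does not say how closely one follows the other.

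The confidence interval would show the strength of correlation, but no rule connects it to the conclusion. Under Protocol 7.2 as written, an observed mean of 0.10 and one of 0.80 lead to the same sentence in the report. That sentence is the trial's primary claim, and Protocol 3.2 expects the data to support authorization in other countries.

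**Working it through.** **Inputs.** From Protocol 7.1: two-sided 0.05, power 0.9, difference 0.1, planning mean 0.8, SD below 0.25 (0.25 used here), 15% drop-out. From SAP 5.5: one-sample t-test with null value 0.

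**Formula.** Power = P(|T| > t(0.975, n−1)), where T is noncentral t with n−1 degrees of freedom and noncentrality (true mean − null value) × √n / SD.

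**1. The plan's own figure.** With 0.1/0.25 = 0.4:
- n = 67: 0.4 × √67 = 3.274, power 0.897.
- n = 68: 0.4 × √68 = 3.298, power 0.902.
- 68/0.85 = 80 enrolled.

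The sample size reproduces. It fits a difference of 0.1, such as 0.8 against 0.7.

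**2. The test as specified, against zero.**
- Smallest significant observed mean, n = 68: 1.996 × 0.25/√68 = 0.0605. At n = 80: 1.990 × 0.25/√80 = 0.0556.
- True mean 0.10, n = 68: the noncentrality is again 3.298, so power is 90.2%. At n = 80 it is 0.4 × √80 = 3.578, and power is 94.2%.
- True mean 0.8: (0.8/0.25) × √4 = 6.4, so four patients already give 98.0% power. The 68 patients therefore do not correspond to the distance from 0.8 to zero.

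**3. Smaller SDs lower the bar further** (n = 68):

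| SD | True mean that rejects zero with 90% probability |
|---|---|
| 0.25 | 0.100 |
| 0.20 | 0.080 |
| 0.15 | 0.060 |
| 0.10 | 0.040 |

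**4. What the planned interval would show** (SD 0.25, n = 68, half-width 0.0605). An observed mean of 0.10 gives about 0.04 to 0.16, and one of 0.80 gives about 0.74 to 0.86. Both exclude zero. The interval separates the two cases and the decision rule does not.

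**5. An optional threshold, illustrated with 0.7.** The lower 95% limit exceeds 0.7 if the observed mean exceeds 0.7 + 0.0605 = 0.761 (n = 68) or 0.7 + 0.0556 = 0.756 (n = 80), at SD 0.25. Probability of passing:

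| True mean, SD | Assumed distribution | n = 68 | n = 80 |
|---|---|---|---|
| 0.80, 0.25 | normal | 90.2% | 94.2% |
| 0.80, 0.25 | left-skewed beta on [0,1] | 86.6% | 91.2% |
| 0.80, 0.25 | left-skewed beta on [−1,1] | 85.6% | 90.2% |
| 0.80, 0.30 | normal | 77.3% | 83.8% |
| 0.80, 0.30 | beta, both ranges | 74% | 79–81% |
| 0.75, 0.25 | normal | 37% | 42% |

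The beta rows come from 200,000 simulated trials each. At a true mean of exactly 0.7 and SD 0.25, the skewed cases pass in 3.3–4.1% of trials instead of 2.5%.

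**6. What the coefficient is.** SAP 5.5 reports 0.871 unshifted and 0.995 after allowing for a shift, with a lag of 10 in both directions. The example in SAP Appendix 7.7 searches lags −15 to +15 and picks out the maximum, 0.984 at lag 8, against 0.943 at lag 0. A maximum over lags is not centred on zero for unrelated waveforms. In an illustrative simulation of 60-second sine waves at 50 Hz (3000 values per minute in Appendix 7.7, 3000/60 = 50), its mean was about 0.05 with independent rates and about 0.30 with equal rates and random phase. These two values depend on the assumed waveforms.

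**The case against.** The case for leaving the plan alone has several parts.

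- **The SAP does not overclaim.** SAP 5.5 states only that independence is refuted, which is what its test can show. This stands. The overstatement is in Protocol 7.2, and a reader should not infer that the SAP shares it.
- **Estimation without a gate is legitimate.** This is an observational study of a CE-marked device, Protocol 7.3 says openly that there is no criterion, and the interval is planned. This stands as an argument against imposing a threshold. It does not rescue Protocol 7.2, which ties its conclusion to rejecting zero and not to the interval.
- **A mean of 0.10 is remote.** The documents plan for 0.8, and their worked examples are 0.995 and 0.984. The 90.2% is the plan's own calculation re-centred on zero, and it carries an SD assumed for a mean of 0.8 over to 0.10. This also stands. A reader might infer that the trial is likely to pass a poorly tracking device, and the documents do not support that.
- **The 0.7 is not a floor.** A reader might take it as a success criterion that the analysis forgot. Protocol 7.1 gives a symmetric planning range around 0.8, and no section makes 0.7 a requirement.
- **A threshold would not show comparability either.** Correlation ignores scale. SAP Appendix 7.2 (step 5) takes two 1-minute files, chosen for a uniform, artifact-free waveform and holding no part of the intervention. This stands, and it is why narrowing the conclusion is the main remedy.

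**Conclusion.** The point holds as a mismatch between rule and conclusion. Protocol 7.2 moves from a mean coefficient different from zero to diagnostic value for long-term monitoring, and the test cannot carry that step. At SD 0.25 an observed mean just above 0.061 (n = 68) or 0.056 (n = 80) would be enough. The 0.1 difference that produced 68 patients has no role in the analysis.

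The figures assume a normally distributed mean and the Protocol's upper-bound SD; a smaller SD makes the rule easier still to meet. They describe what the rule permits, not what the trial is likely to observe.

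A reader might extend the point to the regional conclusion, because the OLV coefficients inherit the zero test. The documents do not support that: Protocol 7.2 rests its regional conclusion on telling normal from single-lung ventilation in a 2×2 table, and the rater analysis in SAP 5.6.1 is unaffected.

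**What to change.** **Main change.**
1. In Protocol 7.2, replace the conclusion with what the test supports: the mean cross-correlation between global impedance and volume waveforms differs from zero in the selected 1-minute segments.
2. In Protocol 7.2 and SAP 5.5, make the planned 95% confidence interval the basis for any statement on strength of agreement.

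**Optional, only if set before any coefficient from this trial is examined.** State in Protocol 7.2 and 7.3 and in SAP 5.5 that a claim of strong waveform correlation requires the lower 95% limit to exceed a justified value. The 0.7 planning bound is one candidate, for the sponsor to justify. Even then, limit the claim to waveform correlation and do not extend it to comparability or diagnostic value.

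**Before any threshold is used.** Reconcile the lag of 10 in SAP 5.5 with the −15 to +15 search in Appendix 7.7. State that the coefficient is the maximum over the chosen lags and report the lag-0 value beside it. Note that such a maximum is not centred on zero under independence.

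**OLV coefficients.** Report them descriptively with their interval, about ±0.11 (n = 22) or ±0.10 (n = 25) at SD 0.25.

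**Cost.** A protocol and SAP amendment, possibly with ethics-committee reappraisal under Protocol section 9. The wording change costs no power and no patients. A 0.7 threshold keeps the planned 90% at 68 evaluable patients only under normality. With left skew power is about 86–87% there, and 90–91% if all 80 are evaluable.

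### Rejecting a zero mean CCF does not show that the device tracks ventilation in most patients, yet Protocol 7.2 concludes it is valuable, and no patient-level summary of the primary CCF is planned

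*SAP*

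**What the plan says.** SAP 5.5 reduces each patient to one coefficient, the average of the CCFs before and after the intervention (or the single one available). It plans a 95% CI for the mean of these patient values. The hypothesis test is stated thus: "a one sample t-test is performed to determine if the mean of the cross-correlation coefficients is significantly different from zero". Protocol 7.2 likewise plans a mean: "The mean value of the intra-subject cross-correlation function (CCF) between global impedance (EIT) waveforms and global volume (ventilator) curves will be determined". It attaches the conclusion to the test: "If the null-hypothesis is refuted the capability of PulmoVista 500 is assumed to be a valuable diagnostic device for long-term monitoring of mechanical ventilation". Protocol 7.3 nevertheless states that pass/fail criteria are not defined.

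Protocol 7.1 sizes the study on another footing. There, "a difference of 0.1 of the mean cross-correlation coefficient shall be detected", with the gloss that "the true value of a calculated mean of 0.8 will not be smaller than 0.7" and an assumed SD below 0.25. The value 0.7 appears only there, as a planning bound for the mean; neither document uses it as a test value.

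For the primary CCF neither document plans a patient-level threshold, a proportion of patients with adequate agreement, or a display of the distribution. The templates for tables, listings and figures (SAP 7.4 to 7.6) are unfilled. Patient-level results are planned elsewhere: a success rate, sensitivity and specificity with confidence intervals for the OLV rater table, and percentages for the questionnaires (SAP 5.6.1).

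**The concern.** A bedside monitor is used on one patient at a time. The t-test sees only the mean, SD and number of the patient coefficients, so the number of patients in whom the device tracked ventilation does not enter the decision. If agreement is high in some patients and absent in others, the test can reject and Protocol 7.2 then calls the device valuable. At stake is whether a positive primary result supports a statement about use in individual patients, and whether the report would show the patients in whom the device did not work.

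**Working it through.** **Plan's own figure.** Inputs from Protocol 7.1: difference 0.1, SD 0.25, two-sided alpha 0.05, power 0.90. One-sample t-test with noncentral t: power is 0.897 at n = 67 and 0.902 at n = 68, so 68 is reproduced, and 68/0.85 = 80. This is the size for a difference of 0.1, not for a mean of 0.8 against zero. For the latter with SD 0.25, 4 patients give 98% power.

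**Set-up.** Of n = 68 patients, k have CCF 0 (failing) and n − k have CCF w (working). Both values are assumptions. With f = k/n:

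- mean = w(1 − f)
- SD = w·√[f(1 − f)·n/(n − 1)]
- lower 95% limit = mean − 1.996·SD/√n, where 1.996 is the t quantile on 67 df.

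**Test against zero, w = 0.95.**

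- 4 working: mean 4 × 0.95/68 = 0.0559; SD 0.2252; SE 0.2252/√68 = 0.0273; t = 2.05; p = 0.045.
- 3 working: mean 0.0419; SE 0.0238; t = 1.76; p = 0.083.

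So 4 working patients suffice, with 64 of 68 (94%) failing. With scatter (working 0.95, SD 0.03; failing 0, SD 0.10; 20,000 simulated trials), the test rejects with probability 1.00 at 50% failures and 0.997 at 80%.

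**Source of the extreme result.** In the same simulation, requiring the lower 95% limit of the mean to exceed 0.7 gives a pass probability of 0.000 at both 50% and 80% failures. The majority-failure result is therefore due to the zero comparator.

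**What the planned CI would show, w = 0.95.** With 34 of 68 failing, the mean is 0.48 (95% CI 0.36 to 0.59). With 54 of 68 failing (79%), it is 0.20 (0.10 to 0.29). Both are far from the planned 0.8.

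**A minority within the planning values.** Take 6 patients at 0 and 62 at 0.88:

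- mean = 62 × 0.88/68 = 0.802
- SD = 0.88 × √(0.0882 × 0.9118 × 68/67) = 0.251
- lower limit = 0.802 − 1.996 × 0.251/8.246 = 0.741.

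The mean and SD match the planning values after rounding (the unrounded SD is just above 0.25), and the limit clears 0.7, with 9% of patients showing no correlation.

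**If the lower limit had to exceed 0.7** (a hypothetical rule, not in the plan), the largest k that still passes at n = 68 is:

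| Working CCF w | Failures k | Share | SD |
|---|---|---|---|
| 0.85 | 6 | 8.8% (1 in 11) | 0.24 |
| 0.90 | 9 | 13.2% (1 in 7.6) | 0.31 |
| 0.95 | 11 | 16.2% (1 in 6.2) | 0.35 |
| 0.984 | 13 | 19.1% (1 in 5.2) | 0.39 |
| 1.00 | 13 | 19.1% (1 in 5.2) | 0.40 |

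Only the first row keeps the SD below the planned 0.25.

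**0.7 as a patient-level mark.** Under a normal distribution with mean 0.8 and SD 0.25, P(CCF > 0.7) = Φ(0.1/0.25) = Φ(0.4) = 0.66. A device performing exactly as planned would have about a third of patients below 0.7.

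**The case against.** The strongest reply has four parts.

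- **The dramatic figures belong to the comparator.** They arise because the test value is zero, not because a mean is used. This stands, as the check with 0.7 shows.
- **The report would not be blind.** The mean and CI are planned, and with half the patients failing they would read about 0.48 (0.36 to 0.59). This also stands: a reader might infer that majority failure would go unseen, and the planned output does not support that. It does not help with a minority. The CI and n give back the SD, but an SD cannot separate a few complete failures from general mediocrity.
- **A threshold of 0.7 on the mean is nobody's rule.** A reader might infer a fixed share of hidden failures, such as one in seven. That is a scenario needing benchmark 0.7, failure at CCF 0 and a working CCF near 0.90, with an SD of about 0.31 against the planned value below 0.25. The documents support only the direction.
- **Patient-level success is planned.** This is true for the OLV rater table and the questionnaires. It is not true for the primary CCF.

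It can also be said that complete failure is unlikely, since the SAP's worked examples give 0.995 and 0.984. Those are single illustrations, and the plan itself allowed for a mean of 0.8 with an SD up to 0.25. Finally, the absence of pass/fail criteria in Protocol 7.3 does not settle the matter, because Protocol 7.2 still draws a conclusion from rejection.

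**Conclusion.** The point holds in a limited form. The test in SAP 5.5 can support a statement about the average correlation; it cannot support the conclusion in Protocol 7.2 about a valuable monitor. Rejection is compatible with 64 of 68 patients at CCF 0 (assuming 0.95 in the rest), though the planned mean and CI would make so large a failure plain.

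The lasting gap is a failing minority, which changing the comparator alone would not close. About 9% complete failures fit the planning values. Under a lower limit of 0.7, 6 to 13 of 68 could pass for a working CCF of 0.85 to 1.0, mostly with an SD above the one planned. These shares depend on the two-group model and are not predictions for this device.

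A reader might also infer that 0.7 should become the patient-level pass mark. The documents do not support this: it is a bound on the mean, and no required proportion of patients is given.

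**What to change.** 1. Reword Protocol 7.2 so that a rejected t-test supports only the statement that the average correlation is above zero, and reconcile it with Protocol 7.3.
2. In SAP 5.5 keep the mean and CI, and add the median, 5th percentile, minimum and a histogram of the patient CCFs.
3. In SAP 5.5 also report, as a descriptive result, the proportion of patients above a CCF cut-off with an exact 95% CI. Fix and justify the cut-off before the analysis. The value 0.7 should not be taken over without its own justification at patient level.

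In the example with 6 failures, any cut-off from 0 up to just below 0.88 would give 62/68 = 91% (exact 95% CI 82% to 97%), which shows what the mean conceals.

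The cost is SAP and protocol wording plus a few lines of output from coefficients already calculated, with no new data or patients. The downside is having to defend a cut-off in advance and possibly a less favourable headline.
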